12.5. Secondary Efficacy Analysis

Demographic and clinical characteristics of the patients will be summarized using frequency counts and percentages, means and standard deviations or medians and interquartile ranges, as appropriate. Best overall response will be summarized as proportion with 95% confidence intervals. Progression-free survival, overall survival, and duration of response will be described by Kaplan-Meier models to plot these endpoints and estimate median times with a 95% confidence interval. Associations of treatment satisfaction and tolerability with HRQOL will be assessed.

12.6. Safety Analysis

Safety will be evaluated according to the CTCAE v4.0. Safety assessments will be based on medical review of adverse event reports and the results of vital sign measurements, physical examinations, and clinical laboratory tests throughout the conduct of the study. Laboratory test abnormalities will be reviewed for clinical significance and only those deemed clinically significant will be reported as adverse events. The MedDRA medical dictionary will be used to map the AE/SAE verbatim terms to specific system organ classes and preferred terms. Frequencies and incidence rates of AEs and SAEs will be tabulated and presented in by-subject listings by system organ classes and preferred term. Summary tables of AEs by grade and body system will be presented.

All adverse events of any grade occurring in the first 48 hours following combinatorial treatment administration will also be assessed as potential infusion reactions. The number and percent of subjects who develop any adverse event consistent with an infusion reaction will be summarized by overall grade.

Early stopping for safety: Data safety and toxicity will be continuously monitored in the study under the guidance from the Data Safety Monitoring Committee. The study will be suspended if there are 1 or more treatment-related deaths within the first 6 patients enrolled during the initial safety assessment, which indicates the treatment-related mortality is $> 5\%$. These treatment-

related deaths must be attributable to direct organ toxicity by study treatment agents with the exception of deaths attributable to immunosuppression (i.e. infections).

12.7. Biomarker Analyses

Serial estimate of biomarker expression will be plotted and summarized over time using means and standard deviations, possibly on a log scale.

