2.2.3. To determine overall survival

2.2.4. To determine the duration of response of these two treatment regimens

[figure not shown]
2.3.Exploratory Objective(s)

2.3.1. To prospectively collect blood and tumor tissue specimens to determine biomarkers of response to treatment with ibrutinib in combination with cetuximab

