7.1.3. Diagnostics/Procedures

1. CT scan of the soft tissue neck and thorax with intravenous contrast for baseline disease assessment. Additional scans (e.g., abdomen/pelvis etc.) may be conducted as needed per each patient's disease burden.
2. Tumor biopsy for correlative testing – A tumor biopsy sample will be collected prior to initiation of study treatment (unless previously archived but new sample preferred) and on cycle 2 day 1 (+/- 7 days)

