7.1.4. Pharmacokinetics/Biomarkers (as applicable)

1. Blood and tumor tissue specimens prior to initiation of study treatment and on cycle 2 day 1 (+/- 7 days) to measure potential biomarkers that can be used to predict response to therapy for an individual patient in future trials.

7.2.Efficacy Evaluations

1. Restaging CT scans will be performed after every 2 cycles and compared to baseline to assess clinical response to study treatment. Response will be determined based on RECIST 1.1 criteria (see section 10).

7.3.Sample Collection and Handling

Blood and tumor tissue specimens will be collected prior to initiation of study treatment and on cycle 2 day 1 (+/- 7 days). These specimens will be collected as part of this protocol and stored in the tissue bank.

Additional peripheral blood and tumor tissue samples may be collected on patients who relapse/progress while in follow-up as part of this protocol. The samples in follow-up are optional.

These samples will be delivered to the tissue procurement core facility at each designated cancer center and processed according to institutional standard operating procedures and frozen.

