11. CORRELATIVES AND BIOMARKER STUDIES

We will prospectively collect blood and tumor tissue specimens to determine biomarkers of response to treatment with ibrutinib in combination with cetuximab. Depending on tissue availability, not all studies may be able to be performed on every specimen.

Planned analyses include:

- Investigate ITK/BTK occupancy in tumor tissue to demonstrate potential therapeutic mechanisms of the combination therapy.
- Multiplex IHC to study the immune microenvironment
- BCR and TCR deep sequencing to identify dominant clone in peripheral blood. This work will be performed by Adaptive Biotechnologies
- Whole exome sequencing, RNAseq/gene expression profiling on baseline tissue to study quantitative evaluation of gene expression patterns and genomic alterations to demonstrate immune checkpoint targets, functional T cell responses, candidate tumor antigens

Analysis will be performed at University of California San Diego. Specimens should be sent to:

[name].

Biorepository Manager,

University of California San Diego, Moores Cancer Center

[name]
[name]
[name]
Office: [contact]
[contact]

Please refer to standard operating procedures for details on assays.

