12.2.3. Exploratory Endpoints

Measurement of biomarkers of ibrutinib and cetuximab response, including BCR and TCR sequencing, immune checkpoint expression, cytokine profiling, gene expression profiling, tumor whole exome sequencing and neoantigen discovery, and to correlate biomarkers to clinical responses

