1. By standard institutional practices. Required only for oropharyngeal and unknown primary tumors
2. Full physical exam at baseline; targeted physical exam at other time points.
3. CBC with Diff: Complete blood count with differential.
4. CMP: Comprehensive metabolic panel (bicarbonate, calcium, chloride, creatinine, glucose, potassium, sodium BUN, albumin, bilirubin total, alkaline phosphatase, total protein, ALT, AST).
5. Pregnancy test for females of child-bearing potential only. Should be obtained with 72 hours of starting therapy and again as indicated
6. Newly obtained tumor tissue collection should be performed when feasible. Otherwise, an archived tumor specimen is adequate.
7. Blood for correlative studies should be collected at the same time blood is drawn for CBC and CMP if possible. 30 ml blood to be collected prior to initiation of study treatment and on cycle 2 day 1 (± 7 days).
8. Imaging for radiographic disease assessment will be performed every 8 weeks (every 2 cycles) following treatment initiation (± 7 days). The same imaging modality should be used throughout the study when feasible. For patients who are clinically stable, a repeat scan will be required 4 weeks (± 7 days) after initial radiographic findings of disease progression as a confirmatory assessment. For CT or MRI, neck and chest should be evaluated; abdomen/pelvis as indicated. If a PET/CT is utilized, CT must be diagnostic quality.
9. Ibrutinib administration will begin 7 days before the start of the second agent and is taken orally on a daily basis.
10. +/- 7 days

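### Section 12.7 summarizes biomarkers only as means and SDs over time, so the planned correlation of markers with response has no stated analysis, and neither tissue source nor patient set is fixed

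*Combined protocol and SAP*

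**What the plan says.** **Aim.** Objective 2.3.1 is "To prospectively collect blood and tumor tissue specimens to determine biomarkers of response to treatment with ibrutinib in combination with cetuximab". Section 12.2.3 lists the markers and adds "and to correlate biomarkers to clinical responses"; the synopsis objectives say the same. Section 7.1.4 gives the purpose of the samples as "to measure potential biomarkers that can be used to predict response to therapy for an individual patient in future trials".

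**Analysis.** Section 12.7 is a single sentence: "Serial estimate of biomarker expression will be plotted and summarized over time using means and standard deviations, possibly on a log scale". The synopsis repeats it. Section 12.5 covers best overall response, PFS, OS, duration of response and HRQOL, but no biomarker. Section 11 lists assays, not analyses.

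**Samples.** Blood is drawn on study before treatment and at cycle 2 day 1 (Section 7.1.2). Tumor is biopsied at the same two times, with the baseline biopsy required "unless previously archived but new sample preferred" (Section 7.1.3). Footnote 6 of Appendix 1 says: "Newly obtained tumor tissue collection should be performed when feasible. Otherwise, an archived tumor specimen is adequate". Exome sequencing and RNA/gene expression profiling are planned on baseline tissue (Section 11). The same section warns: "Depending on tissue availability, not all studies may be able to be performed on every specimen".

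**The concern.** The method does not match the aim. A mean and SD at each time describe the group. They do not say whether patients with high or low values were the ones who responded. Patients are asked for an on-treatment tumor biopsy in support of an objective that has no corresponding analysis. With many assays and few responders, leaving the marker-response comparison to be chosen after the data are seen invites selective reporting.

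There is a second, smaller problem with what 12.7 does specify. For tissue markers measured twice, the baseline value may come from an archived block and the later value from a biopsy on treatment. Section 4.2 allows earlier systemic therapy after a washout, so archived tissue may predate it. For every serial marker, nothing requires the two summaries to come from the same patients. A shift between the two means could then be read as an effect of treatment when part of it is specimen source or selection.

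**Working it through.** **1. Is there a figure to reproduce?** The plan gives no sample size, error rate or effect size for biomarkers. The design figures behind the responder counts below do reproduce:
- Early stopping at a 10% response rate: 0.9^12 + 12 × 0.1 × 0.9^11 = 0.282 + 0.377 = 65.9% (stated 66%).
- Power at 40%, by exact binomial sums for the 1/12 then 5-or-more-of-18 rule: 90.3% (stated 90%).

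**2. Can means and SDs show a link to response?** Take one set of 18 marker values, hence one mean and one SD. If the 7 highest values belong to the responders, the AUC is 1.0. If the 7 lowest do, it is 0.0. The 12.7 summary is identical in both cases.

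**3. Which assays does 12.7 reach?**
- Exome and RNA work: one time point only, so nothing to summarize over time.
- BCR/TCR sequencing of peripheral blood: both samples drawn on study, so no archived/fresh problem. The question of who has a second sample remains.
- Multiplex IHC and ITK/BTK occupancy in tissue: both problems can arise.

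**4. How large could a spurious change be?** All inputs here are assumptions, with no true change in any patient.
- Missing second samples, where the missing patients are 1 SD higher at baseline. Shift = (number missing / 18) × 1 SD: 4/18 = 0.22 SD; 6/18 = 0.33 SD.
- As a rough guide to 4 to 6 missing: Section 1.1.2 gives a median PFS of at most 2.4 months (about 73 days) on cetuximab alone. Cycle 2 day 1 falls 35 days after ibrutinib starts. With exponential times, 1 − 2^(−35/73) = 0.28, and 0.28 × 18 = 5.1 patients with an event. An event does not necessarily mean a missing sample.
- Milder case: responders 1 SD higher, all giving a second sample, with a share k of non-responders doing so. Shift = p/(p + (1 − p)k) − p. For k from 50% to 90%: 0.17 to 0.03 SD at p = 40%, and 0.08 to 0.01 SD at p = 10%.
- Archived baseline. Shift = share archived × offset. From 0.25 × 0.5 = 0.13 SD to 0.75 × 1 = 0.75 SD.

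**5. What does pairing gain?** SE(paired)/SE(unpaired) = √(1 − ρ): 0.84, 0.71 and 0.55 at within-patient correlations of 0.3, 0.5 and 0.7.

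**6. What could a response comparison deliver?** Expected responders: 18 × 0.10 = 1.8 and 18 × 0.40 = 7.2. Simulated power of a two-sided 0.05 exact rank-sum test for one marker (2,000 runs per case, normal marker):

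| Responders of 18 | 1.0 SD | 1.5 SD | 2.0 SD |
|---|---|---|---|
| 2 | 15% | 30% | 53% |
| 5 | 40% | 71% | 92% |
| 7 | 45% | 78% | 96% |

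This is before any allowance for multiple markers. Estimates with intervals are therefore the realistic product.

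**The case against.** The strongest reply is that this is an exploratory objective in 18 patients, or 12 if stage 1 stops with 0 or 1 responses at the interim. No stopping rule, primary analysis or secondary analysis depends on it. The correlation with response is stated as an aim, and a brief descriptive plan is common at this level. Section 12.7 is also compatible with per-patient plots and proposes no before/after test.

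Most of that is fair, and it limits the point. The assumed dropout shifts are also modest. With 14 second samples, the unpaired SE is √(1/18 + 1/14) = 0.36 SD; with 12 it is √(1/18 + 1/12) = 0.37 SD. Shifts of 0.22 and 0.33 SD are below one SE. What the reply does not answer is that no section says how any marker will be set against response.

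A reader might go further and infer three things that the documents do not support:
- That the plan certainly mixes archived with fresh tissue and different patients. New tissue is preferred, and 12.7 is silent on pairing. Mixing is permitted, not prescribed.
- That archived tissue has no age limit. Appendix 1 shows a 42-day window for baseline tissue, although footnote 6 can be read as exempting archived specimens. The text is ambiguous.
- That the whole biomarker program is affected by tissue source. Blood is not, and the baseline-only assays have no change over time to distort.

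**Conclusion.** The concern holds in a limited form. The one stated biomarker analysis contains no response variable, so as written it does not address objective 2.3.1 or endpoint 12.2.3, and it cannot be applied to the baseline-only exome and RNA assays. This conclusion rests on the text alone.

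The comparability point is conditional. For serial tissue markers, an apparent change may partly reflect specimen source. For blood and tissue, it may partly reflect which patients gave a second sample. Under the assumptions shown, the spurious shift runs from 0.01 to 0.33 SD for missing samples and from 0.13 to 0.75 SD for archived baselines. The documents supply no data to narrow these ranges.

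It would be too strong to say that the trial cannot answer its exploratory question. The samples and RECIST responses to be collected would allow a marker-response analysis, at low precision, once one is specified. The primary analysis is unaffected.

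**What to change.** Replace Section 12.7, and the matching synopsis sentence, with:

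1. **Change over time.** Within-patient log ratio (cycle 2 day 1 / baseline) in patients with both samples, reported as a geometric mean ratio with 95% CI, with the number of patients having each sample. For serial tissue markers, the main summary uses pairs whose baseline tissue was newly obtained after the last prior systemic therapy. Archived-baseline pairs are shown separately.
2. **Relation to response.** For each marker, including baseline-only exome and RNA markers, compare baseline values between RECIST responders and non-responders (difference or AUC, with CI). Keep archived specimens in, flagged by source, with a sensitivity analysis excluding them; leaving them out altogether would remove patients from the comparison the objective asks for. Do the same for the paired change where two samples exist.
3. **Recording and labelling.** Record specimen date and site, state whether the 42-day window in Appendix 1 covers archived tissue, name a few priority markers in advance, and label all results hypothesis-generating.

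Do not limit the change analysis to patients progression-free at cycle 2 day 1. The sample falls by day 35 + 7 = 42 after ibrutinib starts, and the first scheduled scan no earlier than day 56 − 7 = 49, so that status would not be known from imaging. Report instead how many patients had clinically documented progression before the sample.

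The cost is SAP wording and two recorded fields. The downside is fewer tissue pairs in the main change summary and wide intervals when responders are few.

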12.8. Interim Analysis

As described above, when 12 patients have been treated in the study, an interim analysis for efficacy will be conducted. This analysis will be completed once the 12th patient has completed their first restaging (after 8 weeks of therapy). It will include any assessments of response performed on patients prior to that time. If there are 1 or fewer responses observed among the first 12 patients at the time of the interim analysis, this study will be discontinued for lack of efficacy. If the null hypothesis is true and the true response rate is 10% or less, the probability of stopping the trial early will be 66%.

13. ADVERSE EVENT REPORTING

Timely, accurate, and complete reporting and analysis of safety information from clinical studies are crucial for the protection of subjects, investigators, and are mandated by regulatory agencies worldwide.

- **Pre-planned or elective hospitalization:** A hospitalization planned before signing the informed consent form is not considered an SAE, but rather a therapeutic intervention. However, if during the pre-planned hospitalization an event occurs, which prolongs the hospitalization or meets any other SAE criteria, the event will be considered an SAE. Surgeries or interventions that were under consideration, but not performed before enrollment in the study, will not be considered serious if they are performed after enrollment in the study for a condition that has not changed from its baseline level. Elective hospitalizations for social reasons, solely for the administration of chemotherapy, or due to long travel distances are also not SAEs.
- **Diagnostic Testing and Procedures:** Testing and procedures should not to be reported as AEs or SAEs, but rather the cause for the test or procedure should be reported.

13.1.3. Serious Adverse Events

A serious adverse event based on International Conference on Harmonisation (ICH) and EU Guidelines on Pharmacovigilance for Medicinal Products for Human Use is any untoward medical occurrence that at any dose:

- Results in death (i.e., the AE actually causes or leads to death).
- Is life-threatening. Life-threatening is defined as an AE in which the subject was at risk of death at the time of the event. It does not refer to an event which hypothetically might have caused death if it were more severe. If either the Investigator or the IND Sponsor believes that an AE meets the definition of life-threatening, it will be considered life-threatening.

- Requires in-patient hospitalization >24 hours or prolongation of existing hospitalization.
- Results in persistent or significant disability/incapacity (i.e., the AE results in substantial disruption of the subject's ability to conduct normal life functions).
- Is a congenital anomaly/birth defect.
- Is an important medical event that may not result in death, be immediately life-threatening or require hospitalization, but may be considered an SAE when, based upon appropriate medical judgment, the event may jeopardize the subject or subject may require intervention to prevent one of the other outcomes listed in this definition. Examples of such events are intensive treatment in an emergency department or at home for allergic bronchospasm, blood dyscrasias, or convulsion that does not result in hospitalization; or development of drug dependency or drug abuse.

13.1.4. Severity Criteria (Grade 1-5)

Definitions found in the Common Terminology Criteria for Adverse Events version 4.03 (CTCAE v4.03) will be used for grading the severity (intensity) of *nonhematologic* AEs. The CTCAE v4.03 displays Grades 1 through 5 with unique clinical descriptions of severity for each referenced AE. Should a subject experience any AE not listed in the CTCAE v4.03, the following grading system should be used to assess severity:

- Grade 1 (Mild AE) – experiences which are usually transient, requiring no special treatment, and not interfering with the subject's daily activities
- Grade 2 (Moderate AE) – experiences which introduce some level of inconvenience or concern to the subject, and which may interfere with daily activities, but are usually ameliorated by simple therapeutic measures
- Grade 3 (Severe AE) – experiences which are unacceptable or intolerable, significantly interrupt the subject's usual daily activity, and require systemic drug therapy or other treatment
- Grade 4 (Life-threatening or disabling AE) – experiences which cause the subject to be in imminent danger of death
- Grade 5 (Death related to AE) – experiences which result in subject death

13.1.5. Causality (Attribution)

The investigator is to assess the causal relation (i.e., whether there is a reasonable possibility that the study drug caused the event) using the following definitions:

| | |
|--------------------------|---|
| Not Related: | Another cause of the AE is more plausible; a temporal sequence cannot be established with the onset of the AE and administration of the investigational product; or, a causal relationship is considered biologically implausible. |
| Unlikely: | The current knowledge or information about the AE indicates that a relationship to the investigational product is unlikely. |
| Possibly Related: | There is a clinically plausible time sequence between onset of the AE and administration of the investigational product, but the AE could also be attributed to concurrent or underlying disease, or the use of other drugs or procedures. Possibly related should be used when the investigational product is one of several biologically plausible AE causes. |
| Related: | The AE is clearly related to use of the investigational product. |

13.2. Unexpected Adverse Events

An “unexpected” AE is an AE that is not listed in the Investigator's Brochure/package insert or is not listed at the specificity or severity that has been observed. For example, hepatic necrosis would be “unexpected” (by virtue of greater severity) if the Investigator's Brochure referred only to elevated hepatic enzymes or hepatitis. Similarly, cerebral thromboembolism and cerebral vasculitis would be “unexpected” (by virtue of greater specificity) if the Investigator's Brochure/package insert listed only cerebral vascular accidents. “Unexpected” also refers to AEs that are mentioned in the Investigator's Brochure as occurring with a class of drugs or as anticipated from the pharmacological properties of the drug, but are not specifically mentioned as occurring with the study drug under investigation.

13.3. Special Reporting Situations

Special reporting situation on a study may require expedited reporting and/or safety evaluation include, but are not limited to:

- Overdose of any study drug
- Suspected abuse/misuse of a study drug
- Inadvertent or accidental exposure to a study drug
- Medication error involving a product (with or without subject exposure to the study drug, e.g., name confusion)

Occurrence of any special reporting situations should be recorded in the eCRF. If any special reporting situation meets the criteria of an AE, it should be recorded on the AEs eCRF. If the AE is considered serious, it should be recorded on the AEs eCRF as serious and should be reported on the Serious Adverse Event Report Form. We will be applying for IND exemption for this

study. If IND exempt, The Serious Adverse Event Report Form should be sent via email or fax to Pharmacyclics Drug Safety or designee within 24 hours of awareness. If not IND exempt, forms will be sent to Pharmacyclics Drug Safety within 15 days of awareness.

